1.0 Objectives

1.1 Study Objectives

Describe the purpose, specific aims or objectives. State the hypotheses to be tested.

Aim 1: To add a cardiovascular health (CVH) module focused on a responsive parenting intervention to the existing perinatal home visitation program delivered by Nurse Family Partnership (NFP) visiting nurses in the Northern Appalachian region of Central Pennsylvania.

Aim 2: To train selected NFP visiting nurses on the CVH module and assess the acceptability of the module as well as the fidelity of delivery to postpartum women and their infants.

Aim 3: To assess the feasibility of using a commercially available actigraphy device to measure infants' sleep in a subset of postpartum women and their infant.

1.2 Primary Study Endpoints

State the primary endpoints to be measured in the study.

Clinical trials typically have a primary objective or endpoint. Additional objectives and endpoints are secondary. The endpoints (or outcomes), determined for each study subject, are the quantitative measurements required by the objectives. Measuring the selected endpoints is the goal of a trial (examples: response rate and survival).

- Successful integration of CVH modules into NFP program during the first 6 months after delivery.
- Good acceptability of the CVH module by NFP visiting nurses and participants.
- Successful consent of 20 postpartum mother-infant dyads into pilot study.

1.3 Secondary Study Endpoints

State the secondary endpoints to be measured in the study.

- Successful data collection related to maternal feeding.
- Successful data collection related to infant sleep.
- Successful data collection related to participant acceptability.

2.0 Background

2.1 Scientific Background and Gaps

Describe the scientific background and gaps in current knowledge.

For clinical research studies being conducted at Penn State Health/Penn State College of Medicine, and for other non-PSH locations as applicable, describe the treatment/procedure that is considered standard of care (i.e., indicate how patients would be treated in non-investigational setting); and if applicable, indicate if the treatment, drug, or device is available to patient without taking part in the study.

Cardiovascular Health of Offspring: A Lifecourse Perspective. Infancy is a critical period of developmental plasticity with long-lasting metabolic and behavioral consequences.^{1,2} Rapid growth during infancy elevates subsequent obesity risk³⁻¹¹ as well as risk for hypertension,¹²⁻¹⁵ coronary heart disease,^{16,17} and diabetes.^{18,19} Unfortunately, population-wide efforts to address these issues to promote CVH have had limited success; 23% of US 2-5 year olds are overweight²⁰ and 9-14% are obese,^{21,22} which underscores the need to prevent obesity and promote CVH during the first 1000 days. The nutritional milieu during critical early stages of development can "program" individuals to develop metabolic syndrome later in life.²³⁻²⁵ These relationships

may be exacerbated among families with overweight parents as genetic and familial influences, combined with pregnancy weight gain are strongly associated with obesity in offspring.²⁶⁻³⁰ Importantly, there are substantial racial, ethnic, and socioeconomic status disparities in obesity and CVD risk factors among children who live in low resource, rural and urban communities such as rural Appalachia.³¹

Home Visitation: An Opportunity for Maternal-Child Cardiovascular Health Promotion. Perinatal HV programs have been utilized domestically and abroad since the 1800s through various models. Most use a multi-visit model encompassing both pre- and postnatal HV. The Nurse-Family Partnership (NFP) program is one of the most well-regarded models,^{32,33} and is one of 21 models meeting federal criteria for evidence of effectiveness.³⁴ NFP serves vulnerable, low income, first-time mothers and seeks to improve health and social outcomes for mothers and infants.³⁵ Women enroll by week 28 of pregnancy, have weekly nurse visits for a month followed by twice monthly visits until delivery. After delivery, dyads are visited weekly for 6 weeks, then twice monthly until the infant is 21 months old. From ages 21 months to 2 years, visits are once per month.

Women who participate in NFP have improved knowledge about contraception, fewer subsequent pregnancies, and more time between pregnancies.³⁶⁻⁴⁰ Infants have fewer emergency visits, unintentional injuries, and poisonings^{38,41,42} with a reduced incidence of child abuse and neglect.^{37,41,43} Years after program completion, the positive effects persist,⁴⁴⁻⁴⁷ resulting in a cost-effective intervention due to less reliance on government-based financial assistance programs.⁴⁸ NFP accounts for contextual factors (e.g., mental health, substance use/abuse, cognitive limitations, etc.) that compromise mothers' abilities to protect themselves and their children, which in part accounts for the program's success. While HV programs cover CVH-related topics (e.g., prenatal diet, weight gain, cigarette smoking, etc.) these programs have not been particularly successful at improving maternal-child CVH. Nonetheless, the visit structure, opportunity for continual refinement, training infrastructure, and quality control mechanisms suggest untapped potential for improving maternal-child CVH.⁴⁹ Further, as suggested by the HRSA supported Home Visiting Applied Research Collaborative (HARC), HV research must evolve to best determine "what works best, for whom, in which contexts, why and how".⁵⁰

Cardiovascular Health and Health Disparities in Appalachia. Appalachia is among the most socioeconomically disadvantaged US regions with marked CVH disparities.⁵¹ Obesity (>30%), smoking (>20%), and physical inactivity (>25%) are more common in Appalachian adults than in the US overall.⁵²⁻⁵⁵ Those in rural Appalachia are more likely to be obese, engage in unhealthy behaviors (i.e., poor diet, physical inactivity, smoking), and have poor mental health than those in metropolitan areas.⁵⁶⁻⁵⁸ As a result, heart disease, stroke, and diabetes are 17%, 14%, and 11% more common in Appalachia than the rest of the US with higher rates of hospitalization and mortality.⁵⁴ Social determinants of health including poor access to preventive care, high rates of generational poverty, and low educational attainment along with reduced access to healthy, affordable foods contribute to the vast health disparities and set the stage for poor CVH.⁵⁹ Addressing social disparities is central to improving CVH and life expectancy.⁶⁰ This proposal targets Northern Appalachia where heart disease mortality is 13% higher than the US rate and 11% higher than the rate in non-Appalachian Pennsylvania.⁶¹ The targeted region contains a dozen HRSA-designated medically underserved areas/populations⁶² and while government-sponsored insurance predominates, hesitancy to enroll in government programs is common, resulting in coverage and care gaps⁶³ that contribute to poor CVH.

Specific to the maternal-child population, women of childbearing age have poorer preconception health with higher rates of obesity, smoking, and poor nutrition compared with non-Appalachian women.⁶⁴ They also have lower rates of annual checkups with healthcare providers. Infant mortality is 16% higher than the national rate, and these rates are higher in the rural counties. School age-children,^{65,66} including those from Northern Appalachia⁶⁷ and children <5 years,^{31,68} are at higher risk of overweight and obesity as compared with non-Appalachian children. This predisposes them to poor CVH across the lifecourse as childhood obesity is associated with adult CVD risk factors⁶⁹ and predicts adult CVD.⁷⁰

2.2 Previous Data

Describe any relevant preliminary data.

Many trials designed for the primary prevention of childhood obesity have been conducted that begin during the first 1000 days.⁷¹⁻⁹⁷ Our responsive parenting (RP)-based Intervention Nurses Start Infants Growing on Healthy Trajectories (*INSIGHT*) trial is arguably the most successful in terms of demonstrating sustained effects on weight status and behaviors associated with CVH (mPIs: [name], [name]).^{92,93} *INSIGHT* is an evidence-based, HV intervention that is implementation-ready for existing home visitation programs like NFP.

INSIGHT enrolled mother-infant dyads during the birth hospital stay, and home interventions (RP vs. safety control) began within a month. The study demonstrated that teaching mothers RP promotes the primary prevention of obesity. Rapid infant weight gain from 0-6 months was reduced in the RP group vs. controls ($p=.004$),⁹⁸ and at 1 year RP group infants were less likely to be overweight (5.5% vs. 12.7%; $p=.047$). As published in *JAMA*,⁹⁹ at age 2 years, RP group children were much less likely than controls to be overweight (11.4% vs. 20.8%, $p=.04$) or obese (0.8% vs. 8.3%; $p=.005$). The study's primary outcome, BMIz at 3 years, was lower in the RP group than control (-0.13 vs. +0.15; $p=.04$). *INSIGHT*'s RP intervention also impacted food parenting associated with child weight by reducing use of "food to soothe"¹⁰⁰ while improving child diets,¹⁰¹ lowering child emotional overeating scores,¹⁰² and increasing child use of self-comforting strategies.¹⁰³ Additionally, the intervention greatly impacted sleep parenting and sleep duration at several time points,¹⁰⁴ important given the strong association between short sleep and adiposity across the lifecourse.¹⁰⁵⁻¹¹¹

INSIGHT is easily adaptable to other home visiting models such as NFP. The RP messages centered on parenting responses to child needs across 4 behavioral states: drowsy, sleeping, fussy, and alert (interactive play and feeding). Although *INSIGHT* delivered guidance at four 90-minute visits in the first year, HV models can be adapted such that guidance is spread out over the first 1000 days.

2.3 Study Rationale

Provide the scientific rationale for the research.

In preparation for a larger, multi-center clinical trial, we aim to pilot adapted versions of part of our prior interventions for delivery within the NFP program visit structure. The population served by NFP in Northern Appalachian counties of Central Pennsylvania could be characterized as higher risk based on demographic variables that include being lower income.

3.0 Inclusion and Exclusion Criteria

Create a numbered list below in sections 3.1 and 3.2 of criteria subjects must meet to be eligible for study enrollment (e.g., age, gender, diagnosis, etc.).

Vulnerable Populations:

Indicate specifically whether you will include any of the following vulnerable populations in this research. You MAY NOT include members of these populations as subjects in your research unless you indicate this in your inclusion criteria because specific regulations apply to studies that involve vulnerable populations.

The checklists referenced below outline the determinations to be made by the IRB when reviewing research involving these populations. Review the checklists as these will help to inform your responses throughout the remainder of the protocol.

- **Children** –Review “HRP-416- Checklist - Children”
- **Pregnant Women** – Review “HRP-412- Checklist - Pregnant Women”
- **Cognitively Impaired Adults**- Review “HRP-417- Checklist - Cognitively Impaired Adults”
- **Prisoners**- Review “HRP-415- Checklist - Prisoners”
- **Neonates of uncertain viability or non-viable neonates**- Review “HRP-413- Checklist - Non-Viable Neonates” or “HRP-414- Checklist - Neonates of Uncertain Viability”

[Do not type here]

3.1 Inclusion Criteria

Create a numbered list of the inclusion criteria that define who will be included in your final study sample (e.g., age, gender, condition, etc.)

Inclusion criteria for this study area are as follows:

1. Mother-infant dyad enrolled in and receiving the NFP program through Geisinger Clinic or UPMC Home Health Care of Central PA
2. Mother age \geq 18 years at time of delivery
3. Mother English speaking
4. Singleton infant born at \geq 35 weeks' gestation
5. Infant age $<$ 1 month at time of consent
6. Reliable access to the internet for consent and data collection purposes
7. Willingness to download and access an app on personal smartphone (subsample of 10 people)

3.2 Exclusion Criteria

Create a numbered list of the exclusion criteria that define who will be excluded in your study.

Exclusion criteria for this study are as follows:

1. Unable or unwilling to comply with the study visits and procedures
2. Participation in a concurrent intervention study
3. Infants with known chromosomal abnormalities, complex congenital heart disease, or birth defects inconsistent with survival to age 2 years
4. Infant with substantial feeding difficulty (e.g., those requiring tube feeding)

3.3 Early Withdrawal of Subjects

3.3.1 Criteria for removal from study

Insert subject withdrawal criteria (e.g., safety reasons, failure of subject to adhere to protocol requirements, subject consent withdrawal, disease progression, etc.).

Participant consent withdrawal and safety reasons (e.g., primary care provider diagnosis of failure to thrive/growth faltering) will be criterion for removal from the study.

3.3.2 Follow-up for withdrawn subjects

Describe when and how to withdraw subjects from the study; the type and timing of the data to be collected for withdrawal of subjects; whether and how subjects are to be replaced; the follow-up for subjects withdrawn from investigational treatment.

Participants may withdraw consent at any time, we will utilize all data collected up to that point. As time allows (~14 month pilot period maximum), we will recruit additional participants for the pilot.

4.0 Recruitment Methods

- Upload recruitment materials for your study in CATS IRB (<http://irb.psu.edu>). **DO NOT** include the actual recruitment wording in this protocol.
- StudyFinder: If StudyFinder (<http://studyfinder.psu.edu>) is to be used for recruitment purposes, separate recruitment documents do not need to be uploaded in CATS IRB. The necessary information will be captured from the StudyFinder page in your CATS IRB study.
- Any eligibility screening questions (verbal/phone scripts, email, etc.) used when contacting potential participants must be uploaded to your study in CATS IRB (<http://irb.psu.edu>).

[Do not type here]

4.1 Identification of subjects

Describe the source of subjects and the methods that will be used to identify potential subjects (e.g., organizational listservs, established recruitment databases, subject pools, medical or school records, interactions during a clinic visit, etc.). If not recruiting subjects directly (e.g., database query for eligible records or samples) state what will be queried, how and by whom.

StudyFinder:

- If you intend to use StudyFinder (<http://studyfinder.psu.edu>) for recruitment purposes, include this method in this section.
- Information provided in this protocol needs to be consistent with information provided on the StudyFinder page in your CATS IRB study.

For Penn State Health submissions using Enterprise Information Management (EIM) for recruitment, and for non-Hershey locations as applicable, attach your EIM Design Specification form on in CATS IRB (<http://irb.psu.edu>). See “HRP-103- Investigator Manual, What is appropriate for study recruitment?” for additional information. **DO NOT** include the actual recruitment material or wording in this protocol.

Participants meeting inclusion/exclusion criteria will be those participating in the NFP program through the Geisinger Clinic or UPMC Home Healthcare of Central PA. Potential participants who are in late pregnancy (≥ 37 weeks' gestation) or recently gave birth to a live infant (within 1 month of delivery) will be identified by visiting nurses and/or their supervisors.

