4.2 Recruitment process

Describe how potential subjects first learn about this research opportunity or indicate as not applicable if subjects will not be prospectively recruited to participant in the research. Subject recruitment can involve various methods (e.g., approaching potential subjects in person, contacting potential subjects via email, letters, telephone, ResearchMatch, or advertising to a general public via flyers, websites, StudyFinder, newspaper, television, and radio etc.). **DO NOT** include the actual recruitment material or wording in this protocol.

[Do not type here]

4.2.1 How potential subjects will be recruited.

Potential participants will be recruited through established partnerships with Geisinger and UPMC Nurse Family Partnership agencies. After potential participants are identified by visiting nurses and/or their supervisors, visiting nurses will share information about the pilot study verbally and through a written summary handout prepared by the study team.

4.2.2 Where potential subjects will be recruited.

Potential participants will be recruited in their homes during regularly scheduled home visits with their visiting nurse from NFP.

4.2.3 When potential subjects will be recruited.

Potential participants will be approached by NFP visiting nurses during late pregnancy (≥ 37 weeks' gestation) or following the birth of a live infant (within 1 month of delivery) at regularly scheduled home visits by NFP visiting nurses. However, enrollment for this pilot study will not occur until after the birth of a live infant (within 1 month of delivery).

4.2.4 Describe the eligibility screening process and indicate whether the screening process will occur before or after obtaining informed consent. Screening begins when the investigator obtains information about or from a prospective participant in order to determine their eligibility. In some studies, these procedures may not take place unless HIPAA Authorization is obtained OR a waiver of HIPAA Authorization when applicable for the screening procedures is approved by the IRB. [For FDA regulated studies, consent for any screening activities would need to be obtained prior to screening unless specifically waived by the IRB.]

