5.2 Obtaining Informed Consent

5.2.1 Timing and Location of Consent

Describe where and when the consent process will take place.

Potential participants will receive information about the study during a regularly scheduled NFP home visit. If eligible and interested in participating, study personnel (NFP nurses) will provide the IRB-approved informed consent form and written consent will be obtained (signed consent and/or electronic consent). NFP nurses will be added as study personnel and will perform the entire informed consent process from explaining the study to obtaining written consent.

We will pilot the feasibility of obtaining written and/or electronic consent. E-consent will be obtained via PSHMC's secure REDCap database and will include electronic signatures and real-time timestamps. REDCap's e-consent framework allows participants to receive a signed copy of the consent form via email or we will print and send a copy upon request.

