7.1 Study Design

Describe and explain the study design.

This is a single arm pilot study in which mother-infant dyads participating in the NFP program will be recruited to assess the feasibility and acceptability of enhancing traditional NFP programming with an experiential intervention focusing on infant sleeping, feeding, and fussing to improve CVH outcomes. Mother-infant dyads will be recruited as previously described.

The experiential intervention will use behavior change strategies (e.g., goal setting, problem solving barriers, expressing empathy) during an interactive, skill-based intervention delivered by trained visiting nurses. During home visits, visiting nurses will provide health coaching as well as print resources to help

participants modify short- and long-term health behaviors. NFP home visiting nurses will document information related to session implementation (e.g., length of visit, quality of delivery, participant engagement).

Four experiential intervention components that focus on improving sleep and responsive feeding practices (i.e., reducing mothers' use of food to soothe non-hunger related distress) and include goal setting and opportunities to practice responsive parenting practices, will be added to increase maternal knowledge and self-efficacy in their use of developmentally appropriate parenting practices and improve CVH outcomes. Intervention content is informed by our prior and ongoing work related to responsive parenting. Messaging will include four content areas: 1) *"Soothing Your Baby"* (e.g., infant temperament, crying norms, soothing strategies that work for your baby, and goal setting), 2) *"Feeding Your Baby"* (e.g., developmentally appropriate infant feeding, feeding on demand/when showing hunger signs, stop feeding when showing fullness signs, avoiding controlling feeding practices, bottle feeding guidance, and goal setting), 3) *"Your Baby's Sleep"* (e.g., bedtime routines for adequate sleep, responding consistently to night waking, and goal setting), and 4) *"Playtime with Your Baby"* (e.g., tummy time, turning off devices during playtime, and goal setting).

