8.0 Number of Subject and Statistical Plan

8.1 Number of Subjects

Indicate the maximum number of subjects to be accrued/enrolled. Distinguish between the number of subjects who are expected to be enrolled and screened, and the number of subjects needed to complete the research procedures if applicable (i.e., numbers of subjects excluding screen failures.)

We anticipate enrolling 20 mother-infant dyads for this pilot study.

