15.2 Feasibility of recruiting the required number of subjects

Indicate the number of potential subjects to which the PSU study team has access. Indicate the percentage of those potential subjects needed for recruitment.

Given the small sample size for this pilot study, it is feasible to recruit the number of subjects needed. Our two NFP agency partners enroll several hundred pregnant women into their programs annually. The Center for Childhood Obesity Research (CCOR) has previous experience recruiting pregnant women and women who have recently delivered and has long standing working relationship with Geisinger and UPMC offices across the state.

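### No order of approach and no record of clients not offered the study: selective offering is possible, and retention, module delivery and participant acceptability may look better than they are

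*Combined protocol and SAP*

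**What the plan says.** Section 4.1 limits the source to clients of two Nurse-Family Partnership (NFP) agencies who are at 37 weeks or later, or within a month after delivery. It says these clients "will be identified by visiting nurses and/or their supervisors". Section 4.2.1 continues: "After potential participants are identified by visiting nurses and/or their supervisors, visiting nurses will share information about the pilot study". Section 17.4 repeats the arrangement and adds that the study team is told of a family once she has been recruited.

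Nurses hold the other roles as well:
- Approach (4.2.3): "Potential participants will be approached by NFP visiting nurses during late pregnancy", or after birth.
- Consent (5.2.1): they "will perform the entire informed consent process from explaining the study to obtaining written consent".
- Delivery and recording (7.1): they deliver the content, and "NFP home visiting nurses will document information related to session implementation", including visit length, delivery quality and participant engagement.

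On numbers, section 8.1 states "We anticipate enrolling 20 mother-infant dyads for this pilot study". Section 8.2 gives no calculation. Section 15.2 says "Our two NFP agency partners enroll several hundred pregnant women into their programs annually". Aim 2 in section 1.1 is "To train selected NFP visiting nurses on the CVH module", and the number of nurses is not given. Section 3.3.2 allows additional participants to be recruited within a pilot period of about 14 months at most. Section 4.2.4 confines screening information to eligibility and keeps it out of the analyses.

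**The concern.** The plan says who spots potential participants but not how one client comes to be offered the study before another. By the time of the offer the nurse knows how each family engages. Section 2.1 has women enrolling by week 28, with weekly visits for a month and then two a month. A woman enrolled at the latest date would have about six scheduled visits behind her at 37 weeks.

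Section 2.3 gives the purpose: to prepare a larger trial in a higher-risk NFP population. Integration of the module and its acceptability are primary endpoints (1.2). Retention and fidelity are planned feasibility summaries (8.3). If the families offered the study are more engaged than the caseload, these figures would mislead the planning of the larger trial. The order of offer also helps to decide which families form the actigraphy subsample, since section 7.2.2 gives the device to the first 10 with home Wi-Fi and a smartphone. A client who was never offered the study leaves no record, so no later analysis could correct this.

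**Working it through.** **1. The text.** Sections 4.1, 4.2.1, 4.2.3, 4.2.4 and 17.4 cover identification, approach and screening. None requires every client in the window to be offered the study, sets a sequence, or asks for a count of those not offered it. Exclusion 1 in section 3.2 (inability or unwillingness to comply) rests on judgement and points the same way.

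**2. Room to choose.** The plan has no figure to reproduce: 20 dyads is stated without a calculation. The number of families within reach would be

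pool = annual enrolment × months/12 × eligible share × share of clients seen by participating nurses.

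Only the 14-month ceiling is in the documents. Recruitment must close earlier, because the last content visit is at 16–20 weeks and section 7.3 runs participation to the six-month visit. The other inputs are assumed: 200–500 enrolled a year, 9–14 recruiting months, 40–80% eligible, and 10–100% of clients with participating nurses. With 60% consent (also assumed), 20/0.6 ≈ 33 families must be approached.

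| Inputs | Pool | 20 as share of pool | 33 as share of pool |
|---|---|---|---|
| 300 × 14/12 × 0.8 × 1 | 280 | 7% | 12% |
| 300 × 14/12 × 0.8 × 0.25 | 70 | 29% | 48% |
| 300 × 14/12 × 0.4 × 0.25 | 35 | 57% | 95% |

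The extremes are 200 × 9/12 × 0.4 × 0.1 = 6 and 500 × 14/12 × 0.8 × 1 ≈ 467. Depending on facts the plan does not give, there is wide room to choose or none.

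**3. What selection could do (illustration; all rates assumed).** Let half of eligible families be easy to retain (90%) and half not (50%). Expected retention is 0.9s + 0.5(1 − s), where s is the easy-to-retain share of those enrolled.

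| s | Expected retention | Bias | P(at least 16 of 20 retained) |
|---|---|---|---|
| 0.50 (as in the caseload) | 0.45 + 0.25 = 70% | 0 | 0.24 |
| 0.75 | 0.675 + 0.125 = 80% | +10 points | 0.63 |
| 1.00 | 90% | +20 points | 0.96 |

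With an easy-to-retain share of 40–60% in the caseload, and rates of 90% against 50% or 95% against 60%, the bias is about +5 to +14 points at s = 0.75 and +14 to +24 points at s = 1.

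**4. Could the data show it?** The exact 95% interval for 16 of 20 is 56% to 94%. It contains both 70% and 90%, so the retention result alone would not reveal selection.

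**The case against.** The strongest reply is that the plan nowhere gives nurses leave to choose. It defines potential participants by objective features and says that they will be approached, so silence on sequence is not a rule of discretion. This stands. A reader might infer that nurses pick families at will, but the documents do not say so. They only leave it open.

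A reader might also infer that 20 easy families can be drawn from several hundred. That is not supported. The figure in section 15.2 is annual programme enrolment across both agencies, before eligibility, refusal, the limit to selected nurses and the shortened recruitment window. With 200–400 a year, 9 months, 60% eligible and a quarter of clients, the pool is 22.5–45, and about 33 approaches would use 74% of the larger figure and exceed the smaller. A middle case goes the other way: of 70 eligible families, half engaged and 60% consenting, 70 × 0.5 × 0.6 = 21 engaged families would consent, enough for all 20 places. The pool size is therefore an open question, and it does not dispose of the concern.

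The biases shown come wholly from assumed inputs, and the largest needs error-free selection. Retention is a descriptive item in section 8.3, not a listed endpoint, and no numeric threshold exists for a bias to tip. Acceptability to the nurses themselves depends on client selection only indirectly. These points limit the size and certainty of the problem.

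Enrolling available clients is also common in a small descriptive pilot. That is fair, but a consecutive offer costs little and cannot be added afterwards.

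**Conclusion.** The gap is real. Identification is left to nurses and supervisors, without an order of approach or a record of clients not offered the study, and nurses also obtain consent, deliver and record. Selective offering could be neither prevented nor detected. Upward bias in retention, module delivery and participant acceptability is possible. It is not established.

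Its size cannot be computed from the documents, because neither the reachable eligible pool nor any retention rate is given, and the percentages above are illustrations only. The conclusion rests on the absence of a rule in the text and on the nurses' prior knowledge of the families. It does not rest on evidence that anyone would select. This is a preventable design weakness that should be closed before recruitment. It does not invalidate the pilot.

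**What to change.** In sections 4.1, 4.2.1 and 17.4, state that each participating nurse offers the study to every client on her caseload who meets the stated timing window, in order of expected or actual delivery date, until the places are filled. Supervisors do not pre-select. The offer comes before any judgement under exclusion 1. The same rule covers additional participants recruited under section 3.3.2.

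Each nurse keeps a de-identified tally of clients due for an offer, offered, and deferred with the reason. Section 4.2.4 should say that these are recruitment counts and not screening information, so that its bar on analysing screening information does not block their use in checking adherence.

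The cost is protocol wording, brief nurse training and a short tally. Some families who might have been skipped must be approached, and the 20 places may fill a little more slowly. The rule does not settle which nurses are trained or how places are shared between the agencies, but tallies kept by nurse would make the latter visible.
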